During the initial funding period of this grant, we tested the hypothesis that the volume and shape of the hippocampus could predict the outcome of treatment with donepezil in patients with very mild-to-mild DAT. The rationale for this experiment was that hippocampal neurons receive cholinergic afferent projections (Umbriaco, et al, 1995), and so became the indirect targets of cholinomimetic treatments. We now propose to extend this investigation of the relationships between neuroanatomical structure and treatment response in patients with DAT by 1) determining what neuroanatomical changes are most strongly correlated with the progression of cognitive deficits in patients with DAT (*Specific Aim 1*), and 2) determining whether treatment with cholinesterase inhibitors and/or adjunctive memantine can slow progression of the neuroanatomical and cognitive/behavioral changes associated with AD (*Specific Aim 2*).

The specific aims and hypotheses of the project are as follows:

Specific Aim 1:

To determine what neuroanatomical measures are most strongly correlated with the progression of cognitive deficits in patients with DAT, we propose to use high resolution magnetic resonance (MR) imaging and the tools of computational anatomy to assess changes in the structure of the hippocampus, parahippocampal gyrus and cingulate gyrus in subjects with very mild-to-mild DAT over two years. During the first funding period of this project, we collected data using MR imaging and large-deformation high dimensional brain mapping (HDBM-LD) that shows that progressive hippocampal volume loss and shape change discriminates subjects with very mild DAT from nondemented controls (see Progress Report). The volume, thickness, and surface area of the parahippocampal and cingulate gyri will be assessed in the proposed work using labeled cortical depth mapping (LCDM), a new computational tool that was developed during the last funding period (see Progress Report). (**Hypothesis 1: Over two years, decreases in hippocampal and cortical volumes, thinning of the cingulate and parahippocampal cortices, and changes in hippocampal shape will be correlated with the rate of cognitive decline in subjects with very mild-to-mild DAT. Moreover, in a stepwise regression**

model, each of these variables will predict the rate of cognitive decline in DAT subjects independently of each other and independently of the effects of age, gender and apoE allelic status.)

Specific Aim 2:

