Variables to assess changes in structural volume, thickness, and shape (for the hippocampus) will be generated as described above. Bivariate correlations between changes in clinical and neuroanatomical variables will be estimated using non-parametric statistics (Spearman's rho). To assess whether observed bivariate relationships are independent of each other, a stepwise multiple regression model will be developed including all independent neuroanatomical variables and slope values for the CDR sum-of-boxes scores as the dependent variable.

To test **hypothesis 2** (*The rate of decreasing hippocampal and cortical volumes, thinning of the cingulate and parahippocampal cortices, and changing hippocampal shape will be equal in DAT subjects that are untreated and in DAT subjects that are treated with donepezil alone, but greater than the rate of volume loss, thinning and hippocampal shape change in DAT subjects that are treated with the combination of donepezil and*

memantine.), rates of change for the various neuroanatomical variables will be compared in DAT subjects that are untreated, that are treated with donepezil alone, that are treated with the combination of donepezil and memantine, and in nondemented comparison subjects. These analyses will be performed using simple difference scores (follow-up minus baseline) for volume and thickness variables. To compare rates of change in hippocampal shape across groups, a MANOVA using eigenvectors derived from the time 1-to-time 2 transformation covariance will be performed (see above). The distributional characteristics of each of these variables will be examined prior to hypothesis testing. Finally, non-parametric (Wilcoxon rank sum tests) statistics will be used to compare the groups.

i. Sample Size and Power Considerations

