Based upon previous work by our group in similar groups of CDR 0.5 and CDR 1 DAT subjects (Berg, et al, 1988; Berg, et al, 1992), and on our experience with the subjects recruited and studied during the initial funding period, we estimate that the attrition rate of subjects who cannot continue in the study for the full two years due to pronounced deterioration, drug side-effects, or refusal to participate will be approximately 20% or less, leaving at least 40 subjects who would provide data for the entire two-year period. However, the number of subjects entered into the analysis may exceed this somewhat, since a slope value can be estimated for each subject who remains in the treatment trial for at least five assessments (one year). Estimating 40 subjects are used in the analysis used to test **Hypothesis 1**, we will have a power of .80 to detect a correlation (or partial correlation) of .44 or more with a 2-tailed significance level of .05 (Borenstein and Cohen, 1988; Kraemer and Thiemann, 1987).

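### The power of .80 for a partial correlation of .44 at N=40 holds for up to about three conditioning variables, not for the fully adjusted claim in Hypothesis 1, where it is about .73 to .77 with shape as a single score

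*Combined protocol and SAP*

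**What the plan says.** Section i (Sample Size and Power Considerations) sets the analysed number from 50 recruits and attrition of "approximately 20% or less, leaving at least 40 subjects". It adds that "the number of subjects entered into the analysis may exceed this somewhat", because a slope can be fitted after one year of assessments. The power sentence itself uses the lower figure ("Estimating 40 subjects are used in the analysis used to test" Hypothesis 1) and claims "a power of .80 to detect a correlation (or partial correlation) of .44 or more" "with a 2-tailed significance level of .05". It gives no number of conditioning variables.

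Under Specific Aim 1, Hypothesis 1 names "decreases in hippocampal and cortical volumes, thinning of the cingulate and parahippocampal cortices, and changes in hippocampal shape" and says that in a stepwise regression "each of these variables will predict the rate of cognitive decline in DAT subjects independently of each other", and also apart from age, gender and apoE status. Section h (Data Analysis) tests the bivariate relations with Spearman's rho. It then tests independence with a stepwise regression of the CDR sum-of-boxes slope, "including all independent neuroanatomical variables". That sentence does not mention the three covariates.

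**The concern.** Power for a partial correlation depends on how many variables are held constant, because each one removes a degree of freedom. A single figure offered for a correlation and a partial correlation alike can be right for both only when that number is small. Hypothesis 1 describes a larger set, and no sentence in the plan gives power for it.

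Aim 1 is meant to find which anatomical measures track decline in their own right. If the team believes the adjusted test has power .80 when it has less, a non-significant adjusted coefficient is easier to misread as showing that a measure adds nothing. The plan does not say it would read results that way. The risk comes from the missing figure.

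**Working it through.** **Inputs from the plan.** N = 40, r = .44, two-sided .05 (section i). Bivariate test: Spearman's rho (section h). Measures in Hypothesis 1: hippocampal volume (1), volumes of two gyri (2), thickness of two gyri (2), hippocampal shape. Covariates: age, gender, apoE (3).

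**Assumption.** Shape enters as one score and each measure as one term (sides not entered separately). That makes 6 measures, so the one under test has 5 others. With the covariates, k = 5 + 3 = 8 conditioning variables.

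**Formula.** Fisher z: power = Φ(atanh(r)·√(N − 3 − k) − 1.96), with atanh(.44) = .4722. The check is the exact bivariate-normal calculation with effective sample size N − k.

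**The plan's own figure first.** For Spearman's rho, use the usual variance factor 1.06: Φ(.4722·√(37/1.06) − 1.96) = Φ(.830) = .797. The rho detectable with .80 power is .442. The stated .44 therefore reproduces for the planned bivariate test.

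**Partial correlation of .44 at N = 40:**

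| k | Conditioning set | Fisher z | Exact |
|---|---|---|---|
| 0 | none (Pearson) | Φ(.912) = .819 | .829 |
| 3 | e.g. age, gender, apoE only | Φ(.794) = .786 | .798 |
| 5 | other anatomical measures only, as section h lists them | Φ(.711) = .762 | .774 |
| 8 | other measures plus the three covariates, as Hypothesis 1 states | Φ(.583) = .720 | .734 |

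A direct least-squares simulation at k = 8, with random predictors mutually uncorrelated or correlated .5, gave .734 to .736. That matches the exact column.

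**Detectable partial correlation at power .80, N = 40 (exact):** about .45 for k = 5 and about .47 for k = 8.

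**Sensitivity to N.** With all 50 recruits analysed and k = 8: Fisher z Φ(.4722·√39 − 1.96) = Φ(.989) = .839; exact .848. By Fisher z, power reaches .80 for r = .44 and k = 8 at N = 47: Φ(.4722·√36 − 1.96) = Φ(.873) = .809.

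**Sensitivity to shape terms, for illustration only.** If shape entered as the 12 coefficients used in the group's earlier longitudinal study, the total would be 5 + 12 + 3 = 20 predictors, so k = 19. Power would then be Φ(.044) = .517 by Fisher z and about .53 by the exact method and by simulation. The plan does not fix that count.

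**The case against.** The best defence is that nothing in the sentence is numerically wrong. Hypothesis 1 names exactly three covariates, and with three the figure is .80. That stands, so a reader who infers an arithmetic slip in the .44 goes too far. It leaves uncovered the part of the hypothesis about independence of the measures from one another.

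The model is stepwise, so the conditioning set is what is retained. With three or fewer other terms power stays near .80. That also stands. But the hypothesis is that every measure contributes, and if it is true the final model should be large.

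N is stated as a floor. At N = 50 the eight-variable case reaches about .85. But 50 would require every recruit to give usable data, and the power sentence uses 40.

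Conventions differ. Cohen's noncentrality f²(u+v+1) gives .80 at k = 5 and .76 at k = 8, so the shortfall narrows but remains for the full claim. The fixed-predictor form f²N gives .85 at k = 8, but it does not suit a population partial correlation with observed predictors, as the simulation shows.

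Three stronger readings are tempting and not supported:

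- **Power is as low as .53 with the plan's own predictors.** The rule of enough eigenvectors for about 75% of variance, in the HDBM-LD section, is for group comparisons. The 12 come from a MANOVA that included nondemented subjects, and that same study went on to use four, or three alongside volume.
- **The simple-correlation threshold should be .43.** That holds for Pearson. The planned test is Spearman, for which .44 is right.
- **Overlap cuts the effective partial correlation to about .19.** This takes the −0.75 between eigenvector 1 and volume change and assumes two measures that each correlate .44 with the slope: (.44 − .44 × .75)/√((1 − .44²)(1 − .75²)) = .185. The −0.75 was computed across DAT and control subjects together and concerns one pair of measures. The group also reports that shape change and volume loss carried complementary information.

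**Conclusion.** The point holds in a limited form. The stated .80 is sound for the bivariate Spearman test and for a partial correlation with up to about three conditioning variables. It is not delivered for the full adjusted claim in Hypothesis 1. At N = 40 power for a partial correlation of .44 is about .77 with the five other anatomical measures and about .73 with age, gender and apoE added, a loss of roughly 3 to 7 percentage points.

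These figures rest on shape as one score, one term per measure, the plan's N of 40, and all terms held in the model together. More shape coefficients, separate left and right measures, or the surface areas also mentioned under Specific Aim 1 would lower them. More analysed subjects or a small retained model would raise them. The documents settle none of these, so no single lower figure can be called the plan's power.

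**What to change.** In section i:

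1. Keep .44 at power .80 for the bivariate Spearman test.
2. Limit the partial-correlation statement to about three conditioning variables.
3. Add one line for the adjusted claim: at N = 40, the partial correlation detectable with .80 power is about .47 with eight conditioning variables, and larger if shape enters as several coefficients. State how many shape terms the regression will use, so that the line can be made exact.
4. Make section h agree with Hypothesis 1 on whether age, gender and apoE are in the regression, since this moves the count between five and eight.

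The cost is a few sentences and a slightly less favourable planning figure. Recruitment, assessments and treatment are unaffected.

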volume were generated across both groups and time as in the cross-sectional study. At baseline, the CDR 0 subjects had a mean (SD) hippocampal volume of 2081(354) mm³ on the left side and 2600 (481) mm³ on the right side, while the CDR 0.5 subjects had a mean hippocampal volume of 1717 (224 mm³) on the left side and 2186 (370 mm³) on the right side. At follow-up, the CDR 0 subjects showed a hippocampal volume reduction of 82 mm³ on the left side and 142 mm³ on the right side, while the CDR 0.5 subjects showed a hippocampal volume reduction of 164 mm³ on the left side and 236 mm³ on the right side. ANOVA indicated a significant group effect on the rate of hippocampal volume loss ($F = 7.81$, $df = 1,42$, $p = 0.008$). This difference persisted after covarying hippocampal volumes for total cerebral brain volume ($p = 0.007$), total intra-cranial volume ($p = 0.008$) and scan interval ($p = 0.015$).

[figure not shown]

Figure 2. Comparisons from Baseline to Follow-up (two years) in CDR 0.5 and CDR 0 Elder Subjects. Displacement maps were used to visualize the across-time difference in hippocampal structure in the two subject groups. Cooler colors (blue to purple) signify areas of inward deformation over time. In the CDR 0.5 subjects, areas of inward deformation were more widespread and included more of the lateral edge of the hippocampus, while in the CDR 0 subjects, areas of inward deformation were smaller and confined to the head

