For the testing of **Hypothesis 2**, we will be measuring the rate of change of neuroanatomical variables over time; therefore, the test-retest reliability for these variables must be high. To estimate the normative test-retest reliability of the neuroanatomical measures proposed in this application, we scanned eight healthy control subjects on two separate occasions approximately one month apart, and then estimated differences between volumes and surface contours of the hippocampus. At the first time point, the mean left hippocampal volume was 2,233 mm³ and the mean right hippocampal volume was 2,699 mm³; at the second time point, these volumes were 2,209 and 2,686 mm³, respectively. Using repeated measures ANOVA, there were no significant test-retest differences in these volumes (on the left $F = .14$, $p = .72$; on the right $F = .07$, $p = .80$) and the intraclass correlation coefficient between these two datasets was very high (ICC = 0.93). To compare the similarity of surface contours at the two time points, we then registered all the scans with respect to the template and then calculated the percent overlap of voxels. The average percent overlap in the eight subjects was 87.4%, which is comparable to the overlap achieved by a single expert performing repeated manual segmentations of the hippocampus from the same MR scan (Haller, et al, 1997). To test the reliability of shape assessment for the hippocampus, we generated the eigenvectors associated with this brain structure based on the eight control subjects at time point 1. The coefficients associated with these eigenvectors were then computed for each subject at both time 1 and time 2. The mean ICC for all eigenvector coefficients was very high - 0.89 (range of 0.83 to 0.94), suggesting very high repeatability. Finally, the standard deviation for the estimation of hippocampal volumes on the two occasions was 225 mm³, and an annual rate of decrease in hippocampal volumes was 2 mm³.

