Assuming that the between-group effect size for comparisons of the rate of change of neuroanatomical variables is moderate (i.e., 0.5 or higher), and if the correlations in neuromorphometric measures within our proposed sample sizes at the different time points continue to be high (i.e., > .75), changes in brain structure shapes of the magnitude observed to date (see Progress Report and Wang, et al, 2003), and volume decreases of 50 mm³ or greater over two years, would be detectable with greater than 85% power (Borenstein and Cohen, 1988; Kraemer and Thiemann, 1987).

HUMAN SUBJECTS

50 new subjects who meet NINDS-ADRDA criteria for probable AD (i.e. DAT), and who have been registered with the MDC for treatment will be recruited for participation in the project during the proposed

funding period. The age range of the subjects will be 50 to 80 years. Any subjects will be excluded if they have medical problems that would contraindicate treatment with donepezil or memantine or make administration of a MR scan or any other aspect of the protocol hazardous.

With regard to the inclusion of both genders and various minorities, the samples will be equally balanced for gender and include approximately 15% African-American subjects. This percentage is similar to the distribution of African-Americans who present to the ADRC and MDC. This distribution of subjects should also allow inclusion of gender as a covariate in data analyses.

2. Collected clinical data will include information about demographics, dementia symptoms, other behavioral disturbances, and performance on tests of cognition (i.e., the ADAS-Cog). In all cases, verbal or written information obtained directly from the patients and involved caregivers will be used. These evaluations will take place in an ordinary office setting. MR scan data will be collected according to established protocols at the Mallinckrodt Institute of Radiology at Washington University.

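### The test-retest figures do not support the stated sensitivity to change: the implied rescan error is about 3 times the 50 mm³ said to be detectable

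*Combined protocol and SAP*

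**What the plan says.** Section i states that Hypothesis 2 measures rates of change, so retest reliability has to be high. For this, "we scanned eight healthy control subjects on two separate occasions approximately one month apart". At the first scan "the mean left hippocampal volume was 2,233 mm³ and the mean right hippocampal volume was 2,699 mm³". A month later the left mean was 2,209 mm³ and the right mean 2,686 mm³. Repeated measures ANOVA gave F = .14, p = .72 on the left and F = .07, p = .80 on the right. The section adds that "the intraclass correlation coefficient between these two datasets was very high (ICC = 0.93") and, later, that "the standard deviation for the estimation of hippocampal volumes on the two occasions was 225 mm³".

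The next paragraph assumes a between-group effect size of 0.5 or more and correlations that "at the different time points continue to be high (i.e., > .75"). It concludes that a decrease of at least 50 mm³ over two years has more than 85% power.

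Section h (Data Analysis) makes the Hypothesis 2 volume variable the follow-up value minus the baseline value, compared between groups. In Preliminary Studies (Assessment of Disease Progression Using Neuroanatomical Markers), "the CDR 0.5 subjects showed a hippocampal volume reduction of 164 mm³ on the left side and 236 mm³ on the right side" over about two years, against 82 and 142 mm³ in CDR 0 subjects.

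**The concern.** A single-occasion ICC compares rescan error with the spread of volumes between people. A difference score removes that spread and keeps the error of both scans. A non-significant mean shift in eight people shows only that the average bias is small relative to its own standard error. Neither tells the reader how noisy one subject's change is, and the section gives no SD or reliability for change.

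Two things depend on this. The Hypothesis 2 power statement needs the SD of change. The Hypothesis 1 correlations use individual change values, which error attenuates, and the stated detectable correlation of .44 makes no allowance for that.

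**Working it through.** **Inputs.** Retest (section i): n = 8; mean shifts 2,233 − 2,209 = 24 mm³ left and 2,699 − 2,686 = 13 mm³ right; F = .14 and .07. Longitudinal study (Preliminary Studies): 18 CDR 0.5 and 26 CDR 0 subjects, F = 7.81 on 1,42 df; baseline SDs in CDR 0 of 354 mm³ left and 481 mm³ right. Group sizes (section a): 21 in Group 1, 38 to 47 in Group 2, about 40 in Group 3. The two-sided .05 level is stated for Hypothesis 1 and assumed here for Hypothesis 2.

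**1. Reproduce the plan's p values.** With two occasions and eight subjects, F has 1,7 df. F = .14 gives p = .719 and F = .07 gives p = .799, matching .72 and .80. The paired reading is therefore right.

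**2. Recover the SD of the rescan difference.** F = n·d²/SD², so SD = d·√(n/F).
- Left: 24·√(8/.14) = 181 mm³.
- Right: 13·√(8/.07) = 139 mm³.
- Rounding of the inputs allows about 171-192 and 124-155.
- The 95% CI on 7 df multiplies by 0.661 and 2.035, giving 120-369 left and 92-283 right.

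**3. Compare with the signals.**
- Two-year loss in untreated CDR 0.5: 181/164 = 1.11 left; 139/236 = 0.59 right.
- CDR 0.5 minus CDR 0: 164 − 82 = 82 left and 236 − 142 = 94 right, so ratios of 2.2 and 1.5.
- The 50 mm³ target: 181/50 = 3.6 and 139/50 = 2.8.

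**4. Is this compatible with an ICC of 0.93?** ICC = 1 − SD²diff/(2·SD²between). With the CDR 0 SDs as a proxy: 1 − 181²/(2·354²) = .87 left and 1 − 139²/(2·481²) = .96 right. These bracket 0.93.

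**5. Total SD of two-year change.** If F = 7.81 was for the average of the two sides, the group difference is (82 + 94)/2 = 88 mm³ and the SD is 88/(√7.81·√(1/18 + 1/26)) = 88/(2.795·0.3066) = 103 mm³. If the F was for one side, the SD would be 96 (left) or 110 (right).

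**6. Power for a 50 mm³ between-group difference.** Power = Φ(50/(SD·√(1/n₁ + 1/n₂)) − 1.96).
- SD 181 (left rescan noise alone): 23% at 40 v 40; 17% at 21 v 40.
- SD 139 (right rescan noise alone): 36%; 27% (26% with the t distribution).
- SD 103 (total change): about 58%; about 43%.
- Lower confidence limits of the rescan SD, 120 and 92: 46% and 68% at 40 v 40.

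For 85% at 40 v 40 the change SD would have to be at most 50/((1.960 + 1.036)·√(2/40)) = 75 mm³, below every value above.

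**7. Where could more than 85% come from?**
- A one-sample change of 50 mm³ in 40 subjects with SD 100 to 103 has 85-87% power, but that is not the Hypothesis 2 comparison.
- An effect size of 0.5 on the raw-volume scale with correlation .75 gives 88-89% at 40 v 40. If 225 were the raw SD, however, that effect is 0.5·225 = 112.5 mm³, not 50.
- With 50 mm³, SD 225 and correlation .75, the change SD is 225·√(2·.25) = 159 and between-group power is 29%.
- The most favourable reading takes 225 as the between-subject SD with correlation .93. The change SD is then 225·√(2·.07) = 84 and power is 76% at 40 v 40 and 60% at 21 v 40.

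**The case against.** The main defence is that sensitivity does not rest on the retest data. The longitudinal study separated 18 from 26 subjects on volume loss (p = 0.008) and on shape change, and Hypothesis 2 compares group means, so individual noise averages out: the standard error of a 40 v 40 difference is 31-41 mm³ on rescan noise alone. This stands for large effects. It does not rescue 50 mm³, because the SD implied by that same study gives about 58%. It is also fair that eight subjects give wide intervals, which is why the lower limits are tested above.

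Some stronger readings are tempting but unsupported:
- *The F values contradict the ICC.* They do not; step 4 shows both can hold. A conflict arises only if 225 mm³ is the between-subject SD (implied ICCs .67 and .81). The text does not say so, and the figure is also close to √(181² + 139²) = 229, the rescan SD of total volume if side errors are independent. It is undefined, not shown to be wrong.
- *The left side fails the >.75 condition.* That rests on the same reading of 225, and the condition concerns the trial groups, not eight controls.
- *Change reliability is near zero.* Averaging the sides gives noise of 229/2 = 114 mm³ against 103, so 1 − (114/103)² is negative, which is impossible for a true reliability. It shows imprecise inputs or failed assumptions (independent side errors, F on the side average). Allowing for sampling error in both SDs, values up to about two thirds are possible.
- *Noise equals the two-year loss.* This is true on the left only.

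Using the left-right average, or extending the retest work to shape change and the cortical measures, may be useful but is not needed to settle this point.

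**Conclusion.** The point holds in limited form. The section asks for reliability of change and supplies evidence about single-occasion volumes. Its own figures imply a rescan-difference SD of about 181 mm³ left and 139 mm³ right, larger on both sides than the difference between CDR 0.5 and CDR 0 losses and about 3 times the 50 mm³ target.

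The claim of more than 85% power for 50 mm³ is not reproduced for the between-group comparison under any reading tried. It is 23-36% at 40 v 40 on per-side rescan noise alone, about 58% on an SD of 103 mm³, and 76% on the most favourable reading of the 225 mm³. Real variation in atrophy between patients can only lower the noise-only figures.

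This rests on two-sided .05 for Hypothesis 2, on the 50 mm³ being a between-group difference on the scale of one side or the side average, on error in healthy controls resembling error in patients, and, for the 103 mm³, on the F being for the side average. The documents do not show that any reported number is false, or that the measure cannot detect large group differences.

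**What to change.** In section i:
- Report the SD of the rescan difference for each side, with its confidence interval, from the eight scan pairs already held.
- State what the 225 mm³ is the standard deviation of.
- Stop citing the cross-sectional ICC as evidence that change is measured reliably.
- Restate the detectable difference and power from the SD of the change score at the actual group sizes, saying whether the 50 mm³ is a within-group or between-group quantity. For scale, at 85% power an SD of 103 mm³ gives a detectable difference of 2.996·103·√(2/40) = 69 mm³ at 40 v 40 and 2.996·103·√(1/21 + 1/40) = 83 mm³ at 21 v 40.

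The cost is a reanalysis of existing scans and revised text, with no new subjects or scans. The downside is that the stated sensitivity becomes less favourable.

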We have recently replicated the results of our first study of hippocampal structure in DAT in a larger, non-overlapping group of 46 subjects with DAT and 65 non-demented controls (Csernansky, et al, in preparation). The DAT and non-demented subjects were again matched with regard to gender (20/26 [m/f] for the DAT subjects and 19/46 [m/f] for the non-demented subjects) and age (mean (SD) 74.6 (7.9) years for the DAT subjects and 78.2 (7.7) years for the non-demented subjects). The mean (SD) sum-of-box score derived from the CDR was 4.05 (2.04) for the DAT subjects, indicating that the subjects had very mild-to-mild dementia. The non-demented subjects had a mean (SD) hippocampal volume of 2142 mm³ (344) on the left and 2588 mm³ (416) on the right, while the DAT subjects had a mean (SD) hippocampal volume of 1833 mm³ (359) on the left and 2242 mm³ (462) on the right.

Analysis of variance (ANOVA) showed that the difference in hippocampal volumes between these two subject groups was highly significant ($F = 21.38$, $df = 1,109$, $p < .0001$). As in our first study (Csernansky, et al, 2000),

[figure not shown]

Figure 1. Visualizing the pattern of hippocampal surface deformation associated with DAT. The left and right hippocampi are viewed from above and to the right of the paired structures. The structure seen represents the composite hippocampus of the non-demented subjects and the shading indicates the degree of displacement of the hippocampal surface that was present in the DAT subjects (cooler colors (e.g. blue) represent inward deformation and warmer colors represent outward deformation). Areas of blue shading indicate regions of the hippocampal surface where there is localized volume loss (i.e., inward deformation) in the DAT subjects.

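### The claimed power above 85% for a 50 mm³ two-year volume change is not reached, on the protocol's own figures, by any between-group comparison in Hypothesis 2 at two-sided .05

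*Combined protocol and SAP*

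**What the plan says.** Study Design, h (Data Analysis) tests Hypothesis 2 by comparing untreated, donepezil, combination and nondemented subjects. Volumes are analysed as follow-up minus baseline. Study Design, a gives the group sizes: 21 untreated, 38 (possibly 47) donepezil, and about 40 combination after attrition.

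Study Design, i first reports a reliability exercise: "we scanned eight healthy control subjects on two separate occasions approximately one month apart", and "the intraclass correlation coefficient between these two datasets was very high (ICC = 0.93"). It closes with "the standard deviation for the estimation of hippocampal volumes on the two occasions was 225 mm³". It does not say whether this is the SD of the volumes, of measurement error or of a difference, nor whether it is per side or total.

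The next paragraph assumes that "the between-group effect size for comparisons of the rate of change of neuroanatomical variables is moderate (i.e., 0.5 or higher") and that correlations "at the different time points continue to be high (i.e., > .75"). From this it concludes that a 50 mm³ decrease over two years is detectable with more than 85% power. It gives no SD of change, contrast, alpha or group sizes. A two-sided .05 level is stated only for Hypothesis 1.

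The one longitudinal data set is in Preliminary Studies (Assessment of Disease Progression): two-year losses in 18 CDR 0.5 and 26 CDR 0 subjects, with "ANOVA indicated a significant group effect on the rate of hippocampal volume loss ($F = 7.81$, $df = 1,42$, $p = 0.008").

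**The concern.** Power for a comparison of difference scores depends on the SD of two-year change in DAT subjects. The power section does not report it. The one SD it does report comes from the wrong population and the wrong interval for that purpose, whichever way it is read. The stated power therefore cannot be checked from the section, and the figures elsewhere in the protocol point lower.

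Hypothesis 2 is the treatment question. If the power for 50 mm³ is nearer 40-60% than 85%, a null result for the combination says little. A reader relying on the stated figure would take it as evidence against an effect of that size. The hypothesis also predicts equality of untreated and donepezil subjects, so an overstated sensitivity would lend false weight to a null finding there too.

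**Working it through.** **Method.** Two-sample t test, two-sided .05 (assumed to carry over from Hypothesis 1), power from the noncentral t. The noncentrality is d / √(1/n₁ + 1/n₂), with d = 50 mm³ / SD of change. The root term is 0.215 for 40 v 47, 0.227 for 40 v 38 and 0.269 for 40 v 21.

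**1. The section's own effect size, d = 0.5.** For 40 v 47 the noncentrality is 0.5/0.215 = 2.32 against a critical value of 1.99, giving 63%. The other contrasts give 59% (40 v 38) and 45% (40 v 21). This needs no SD, and it does not reproduce 85%. About 73 per group would be needed.

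**2. The 225 mm³, read as the SD of volumes at one time.** SD of change = 225 × √(2(1 − r)).
- r = .75: 159 mm³, d = 0.31.
- r = .93 (the volume ICC, the most favourable volume correlation reported): 84 mm³, d = 0.59.
- Read instead as the SD of change itself: d = 50/225 = 0.22.

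**3. The SD of change implied by the pilot.** For two groups, SD = difference in mean loss / √(F × (1/18 + 1/26)). With F = 7.81 the denominator is √(7.81 × 0.0940) = 0.857. F = 7.81 on 1 and 42 df gives p = 0.0078, which agrees with the stated 0.008.
- Left: (164 − 82)/0.857 = 96 mm³.
- Right: (236 − 142)/0.857 = 110 mm³.
- Mean of sides: 88/0.857 = 103 mm³.
- Sum of sides: 176/0.857 = 205 mm³.

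**Power for 50 mm³**

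| Input | 40 v 47 | 40 v 38 | 40 v 21 | One group, n = 40, before-after |
|---|---|---|---|---|
| d = 0.5 | 63% | 59% | 45% | 87% |
| SD 225, r = .75 | 30% | 28% | 21% | 49% |
| SD 225, r = .93 | 78% | 74% | 58% | 96% |
| 225 as SD of change | 18% | 16% | 13% | 28% |
| Pilot, 96 (left) | 67% | 62% | 48% | 90% |
| Pilot, 103 (mean) | 61% | 56% | 43% | 85% |
| Pilot, 110 (right) | 55% | 51% | 38% | 80% |
| Pilot, 205 (sum of sides) | 20% | 19% | 14% | 32% |

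Pooling both comparator groups (40 v 68) at SD 225 and r = .93 still gives only 84%. With the pilot SD of 103 mm³, the difference detectable with 85% power is about 67 mm³ (40 v 47), 71 mm³ (40 v 38) and 84 mm³ (40 v 21).

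**The case against.** Several points can be made for the plan.

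**The claim may be within-group.** It speaks of volume decreases, and a before-after test in 40 subjects has 80-90% power on the pilot SD (per side or mean of sides). That may be how the figure arose. But the same sentence assumes a between-group effect size, and section h compares groups, so this is not the Hypothesis 2 test.

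**The effect size may be in SD units of volume, not of change.** With r = .75, 0.5 becomes 0.5/√0.5 = 0.71 on the change scale, giving about 90% (40 v 47) and 87% (40 v 38), though 73% for 40 v 21. With an SD of 225 that effect is 112.5 mm³, not 50.

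**The correlation is a floor, and the hypothesis is directional.** At SD 225, 85% needs r of about .94 (40 v 47) or .95 (40 v 38), above any volume correlation reported. A one-sided .05 test at r = .93 would just pass for 40 v 47: 0.594/0.215 = 2.76, less 1.66, is 1.10, or about 86%. No one-sided test is planned.

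**The pilot SD is fragile.** This stands. It pools 18 CDR 0.5 with 26 nondemented subjects, and one F is applied to either side in turn. The F concerns a rate, and mean intervals were 2.0 and 2.2 years. Annualising the losses and doubling (left 2 × (164/2.0 − 82/2.2)/0.857, right likewise) gives 104-125 mm³, mean 115, and power of 52%, 48% and 36%. The value 7.81 also appears in the pilot's shape analysis, on 4 and 39 df. These points make the replacement figures provisional, but none lifts a between-group comparison to 85%.

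**Two stronger readings that a reader might infer are not supported.** The first is that 225 mm³ is an SD of volumes and is the source of the error. The power paragraph never cites it, and at r = .75 it does not produce 85% under either test. The retest results ("on the left $F = .14$, $p = .72$; on the right $F = .07$, $p = .80") with mean differences of 24 and 13 mm³ in eight subjects imply difference SDs of 24 × √(8/.14) = 181 and 13 × √(8/.07) = 139 mm³. With ICC .93 the volume SDs would then be 181/√.14 = 485 and 139/√.14 = 371, not 225.

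The second is that power is lower still because "the DAT subjects had a mean (SD) hippocampal volume of 1833 mm³ (359) on the left and 2242 mm³ (462) on the right". Turning those into SDs of change needs a two-year correlation in DAT that the protocol does not report. Borrowing the one-month control ICC gives 359 × √.14 = 134 and 462 × √.14 = 173 mm³, which conflict with the pilot's 96-110.

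**Conclusion.** The claim is wrong as written for the comparisons that Hypothesis 2 makes. At two-sided .05, power for 50 mm³ is 45-63% on the section's own effect size. On the pilot's SD of change it is about 51-67% for combination versus donepezil and 38-48% for combination versus untreated. The most favourable reading of the 225 mm³ gives 78%.

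The pilot-based figures assume that the F test used each subject's two-year loss per side or averaged over sides, with a common within-group SD. If it used left plus right totals, power for 50 mm³ of total volume is only about 14-20%. The rank tests named in section h would lower all of these slightly. The finding concerns the volume claim, not the shape claim in the same sentence. It does not establish where the 85% came from.

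**What to change.** In Study Design, i, base the volume power on the observed SD of two-year hippocampal volume change, left and right, in DAT subjects already scanned twice: the 18 pilot CDR 0.5, the 21 untreated and the 38 donepezil subjects. Any pilot subjects who are also among the 21 should be counted once. State the contrast, alpha, sidedness and group sizes. Replace the 85% claim with the resulting power for 50 mm³, or with the difference detectable at 85%.

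Until that is done, the published F supports only provisional values: about 56-61% for combination versus donepezil and 43% for combination versus untreated, or about 67-84 mm³ detectable. The 225 mm³ may stay as a reliability result if it is defined.

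The cost is one calculation on data already held and a less favourable stated power. Enrolment and procedures do not change.
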